Serial Movement in Collegiate Athletes who perform Injury Prevention Training

NCT04748718

03/28/2024

Study Protocol

Objective

The overall objective of the study was to longitudinally evaluate multiple aspects of neuromuscular control (i.e., movement quality, balance) across several time points during a single athletic season in collegiate athletes who perform neuromuscular training.

Design

We used a prospective, experimental case series study design to evaluate neuromuscular control over an athletic season in collegiate athletes performing PTPs. We collected neuromuscular control data at three time points (PRE, MID, POST) during each athletic season. PRE occurred during the first two weeks of the athletic season, MID occurred during the middle of the athletic season, and POST occurred during the last two weeks of the athletic season.

Methods

Athletes age 18+ on the men's and women's volleyball, soccer, and basketball teams at one NCAA Division III University were recruited to volunteer for this study. All participants completed informed consent forms, which were approved by the University's Institutional Review Board.

LESS score was attained using a valid and reliable 2-dimensional motion capture system (Physimax Technologies, Tel Aviv, Israel) that utilizes an Xbox Kinect camera (Microsoft, Redmond, WA) and Dell (Round Rock, TX) laptop computer to automate LESS score. BESS score was attained using a pressure mat and associated software that automatically scores all 6 BESS stances (TekScan, Boston, MA), a system which has been shown to be a reliable method to assess the BESS. Participant height was measured using a standard stadiometer. Participant mass was measured using a digital scale. Participant age, race, and ethnicity were captured using a pen-and-paper questionnaire. Gender was determined by team participation.

Participants completed three test sessions, all of which included a jump-landing task, scored by the LESS, to assess movement control and the BESS to assess balance. At the first test session, participants' height and mass was also measured. All tasks (LESS, BESS, height, mass) were completed in a random order. All test session occurred prior to team practices.

For the LESS, participants were instructed to jump forward off a 30-cm-high box to a distance of approximately half their height, indicated by a line on the floor, and then jump up for maximal vertical height immediately upon landing. Participants jumped as many times as needed to record three good trials, up to five total jumps. Errors were automatically scored using a 2-dimensional motion capture system described in materials. For the BESS, participants completed six total conditions, consisting of 3 stances (double-limb stance, single-limb stance, tandem stance) on 2 surfaces (firm,

foam). For each condition, participants are instructed to maintain the appropriate stance on the appropriate surface for 20 seconds. Errors were automatically scored using the pressure mat described in materials.

Statistical Analysis Plan

The mean LESS score for three trials was used for analyses. BESS score was calculated by summing scores from all six conditions. We used a 2X3 ANOVA to evaluate changes in LESS and BESS over time (PRE, MID, POST). As previous research has shown variability in neuromuscular control measures over time in athletes that do not perform PTPS, we used a multivariate correction for these analyses. Post hoc pairwise comparisons were evaluated for significant results using 95% confidence intervals.

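### Does the random task order, which lets the first LESS jump come before height is measured, undermine the comparison of LESS over the season?

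*Combined protocol and SAP*

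**What the plan says.** Three statements in the Methods of the Study Protocol meet at this point.

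- Height belongs to the first session and has one named instrument: "At the first test session, participants' height and mass was also measured", and "Participant height was measured using a standard stadiometer".
- Height has no fixed place among the tasks: "All tasks (LESS, BESS, height, mass) were completed in a random order".
- The LESS landing line depends on height. Athletes jump from the box "to a distance of approximately half their height, indicated by a line on the floor".

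The LESS is repeated through the season: "Participants completed three test sessions, all of which included a jump-landing task". The Statistical Analysis Plan takes the mean of three LESS trials per session and tests change over PRE, MID and POST in a 2X3 ANOVA. It adds: "Post hoc pairwise comparisons were evaluated for significant results using 95% confidence intervals".

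The text does not say which height was used to place the line. Nor does it say whether an athlete's distance was written down at PRE and used again at MID and POST.

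**The concern.** Read literally, the ordering rule allows a step to come before the measurement it depends on. An athlete drawn to do the LESS before height has no stadiometer reading yet, so the PRE line must rest on something else, such as a reported height or a judgement by eye. At MID and POST a measured height is on file. If staff then moved the line to match it, the athlete would do a slightly different task at PRE than later.

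Change in LESS over time is a planned analysis, so a set-up difference between PRE and the later sessions would fall on the very factor being tested. The study is a case series and describes no control group, so no parallel series would show that the set-up, and not the athletes, had changed. BESS does not depend on height and is not involved.

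**Working it through.** The documents give no figure for this point, so there is nothing to reproduce. The check has four steps.

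**Inputs.** From the Methods: four tasks in random order at the first session, a line at about half of height, and three LESS sessions. Assumed, because the documents give no values: equally likely orders, athlete heights, and the error *e* in any height that was not measured.

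**1. How often the rule allows LESS before height.** There are 4! = 24 orders. By symmetry LESS comes before height in half of them: 24 / 2 = 12, or 50%. With height fixed first there would be 3! = 6 orders, none of them with LESS before height. The 50% is how often the rule permits the sequence. It is not how often a line moved, which is unknown and may be zero.

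**2. How far the line would move.** The line is at height / 2, so a height error *e* shifts it by *e* / 2.

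| Assumed *e* | Shift *e* / 2 | Assumed heights (line) | Shift as % of line |
|---|---|---|---|
| 1 cm | 0.5 cm | 160–190 cm (80–95 cm) | 0.5/95 = 0.5% to 0.5/80 = 0.6% |
| 3 cm | 1.5 cm | 160–190 cm (80–95 cm) | 1.5/95 = 1.6% to 1.5/80 = 1.9% |
| 5 cm | 2.5 cm | 160–200 cm (80–100 cm) | 2.5/100 = 2.5% to 2.5/80 = 3.1% |
| 10 cm | 5 cm | 160–200 cm (80–100 cm) | 5/100 = 5.0% to 5/80 = 6.3% |

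The percentages follow from the choice of *e*; the documents do not narrow it.

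**3. Which comparisons could be touched.** This depends on practice that the text does not describe.

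- *Same height or same distance at all sessions.* The line is constant within each athlete, even if it is not exactly half of height. The set-up difference is 0 in every comparison.
- *Unmeasured height at PRE for athletes who did LESS first, measured height afterwards.* PRE–MID and PRE–POST could carry a shift of *e* / 2 in those athletes. MID–POST carries none.
- *Line estimated afresh each time.* Any pair of sessions could differ, MID–POST included.

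**4. What reaches a mean difference.** Take the second case, with half of the athletes affected. The mean shift over all athletes is ½ × mean(*e*) / 2 = mean(*e*) / 4, where *e* carries its sign.

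- If every error is 1 to 3 cm in the same direction, the mean shift is 0.25 to 0.75 cm, or 0.25/95 = 0.3% to 0.75/80 = 0.9% of the line.
- If errors fall evenly on both sides, mean(*e*) is 0 and so is the mean shift. What remains is some added variation within athletes.

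A shift in centimetres cannot be converted into LESS points from these documents.

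**The case for a change.** The best case for a change is that the gap exists only at PRE, which makes it differential over time. Reported heights might all err the same way, so cancellation cannot be taken for granted. The remedy is also simple: with height first, the count falls from 12 of 24 to 0 of 6, and LESS still comes before BESS in 3 of those 6 orders, so the order of the two tests stays balanced.

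Much of this stands. The mechanism is real, the counts are right, and a later study would lose little by measuring height first. It still does not support a change here, for four reasons.

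- The protocol describes the sessions as completed. Reordering cannot alter these data.
- Nothing is contradicted. The distance is set only approximately, and a line placed from a reported or estimated height can meet that wording.
- Reordering would not by itself secure the comparison over time. What matters is that each athlete's distance stays the same, and that can be done with or without a stadiometer reading at PRE. It needs the distance to be stored and retrieved at two later sessions, which costs little but not nothing.
- No different analysis follows. Leaving out PRE would discard the baseline of the time comparison to guard against a shift that nobody has shown.

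**Conclusion.** No change to the plan is called for. The ordering sentence does let the first LESS jump come before the height measurement, in 12 of 24 orders if all are equally likely. The consequence needs two further steps: a height in error at PRE, and a line moved afterwards. The documents show neither. If both occurred, height errors of 1 to 3 cm would move the line by 0.5 to 1.5 cm (0.5% to 1.9%) in the affected athletes. The mean over all athletes would move by no more than 0.75 cm, and that only if every error had the same sign.

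These sizes rest on assumed heights and errors. With an assumed error of 10 cm the line moves 5 cm (5.0% to 6.3%), so the judgement that the effect is small depends on staff having had a reasonable idea of each athlete's height. The effect on the LESS score itself cannot be computed.

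This is a missing detail of set-up in a very short protocol. The investigators can state in the study report which height placed the line at each session and whether each athlete's distance stayed constant. If it did, the question is closed for all three LESS comparisons.

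### Does the unnamed two-level factor in the 2X3 ANOVA mean that LESS and BESS were pooled into one test of time?

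*Combined protocol and SAP*

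**What the plan says.** The model is given in one sentence of the Statistical Analysis Plan: "We used a 2X3 ANOVA to evaluate changes in LESS and BESS over time (PRE, MID, POST". The next sentence adds: "As previous research has shown variability in neuromuscular control measures over time in athletes that do not perform PTPS, we used a multivariate correction". No test statistic, family of tests or omnibus alpha is given. Follow-up is described as "Post hoc pairwise comparisons were evaluated for significant results using 95% confidence intervals".

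The two scores are built differently. For LESS, "The mean LESS score for three trials was used for analyses". For BESS, "BESS score was calculated by summing scores from all six conditions". No standardisation is described.

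Two other places bear on the missing factor. Methods recruits from men's and women's teams and states "Gender was determined by team participation". The Objective is to "longitudinally evaluate multiple aspects of neuromuscular control (i.e., movement quality, balance) across several time points during a single athletic season", so movement quality and balance appear as distinct aspects.

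**The concern.** LESS and BESS are the only pair in the ANOVA sentence, and the Statistical Analysis Plan never mentions gender. Read literally, the model could be measure by time. The time main effect would then be a test on the average of two scores in different units, and the interaction a test on their difference. Neither aspect in the Objective would have its own time test. A change in LESS could be hidden by the noise in BESS, a time effect could come from BESS alone, and intervals following a significant time effect would describe a mixture.

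The undefined correction adds to the doubt. It could be a multivariate repeated-measures statistic, a joint test of both outcomes, a sphericity correction or an adjustment of alpha. The wording alone does not settle what was tested.

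**Working it through.** The documents give no sample size, alpha for the ANOVA, SD, correlation or power, so there is no figure of theirs to reproduce. Every numerical input below is an assumption.

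**1. What pooling would cost.** Let k be the SD of within-person change in BESS divided by that in LESS, and c the correlation between the two changes. If only LESS shifts, the sum and the difference of the scores carry the same mean shift as LESS but more variance. The share of LESS information kept is:

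- time main effect: 1/(1 + k² + 2ck)
- interaction: 1/(1 + k² − 2ck)

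| k | c = 0, either term | c = 0.3, time | c = 0.3, interaction |
|---|---|---|---|
| 1 | 1/2 = 50% | 1/2.6 = 38% | 1/1.4 = 71% |
| 2 | 1/5 = 20% | 1/6.2 = 16% | 1/3.8 = 26% |
| 3 | 1/10 = 10% | 1/11.8 = 8.5% | 1/8.2 = 12% |

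A range of 10% to 50% is therefore exactly k = 1 to 3 with c = 0. At c = 0, k = 0.5 gives 1/1.25 = 80% and k = 5 gives 1/26 = 3.8%. The documents do not say where k lies.

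**2. The same in power.** Assume N = 80, LESS means of 0, 0.15 and 0.30 SD, within-person correlation 0.6 and alpha 0.05. The deviations from the overall mean are −0.15, 0 and 0.15, so the noncentrality for LESS alone is 80 × (0.15² + 0.15²)/(1 − 0.6) = 80 × 0.045/0.4 = 9.0. With F on 2 and 78 degrees of freedom, power is 75%.

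At c = 0 the pooled time test divides 9.0 by 1 + k²:

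| k | Noncentrality | Power, pooled time test | Power, time or interaction (simulated) |
|---|---|---|---|
| 1 | 4.5 | 45% | 69% |
| 2 | 1.8 | 20% | 38% |
| 3 | 0.9 | 12% | 23% |

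The last column matters because a 2X3 ANOVA tests both terms, and the interaction also responds to a change in LESS alone. At k = 1 and c = 0.3, simulations put the two terms together at 73% to 75%, so almost nothing is lost. A large loss needs k of about 2 or more.

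**3. Gender by time, one model per score.** Nothing is pooled. The noncentrality for LESS stays at 9.0, and simulation with two equal groups gives 75.6% power for time, the same as LESS alone.

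**4. A joint test of the separate LESS and BESS contrasts.** Such a test does not depend on the units of either score, so the different scales do no harm.

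**5. Error rates under gender by time.** If each test is made at 0.05, each holds about 5%. Time and interaction together give 1 − 0.95² = 9.75% within one score (9.5% to 10.1% in simulation). Four tests over two independent scores give 1 − 0.95⁴ = 18.5%. Simulation gives about 18% at a LESS–BESS correlation of 0.3 and 16% at 0.7. An adjustment of alpha, if that is what the correction was, would lower these figures.

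**6. Which reading the text supports.**

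- For measure by time: LESS and BESS are the only pair in the sentence.
- Against it: the scores are defined in separate sentences, the Objective treats them as separate aspects, and "we used a multivariate correction for these analyses" is plural, where a measure by time model would be one analysis.
- For gender: it is the only clearly two-level participant variable recorded.
- The reason given for the correction, variability over time, suits a multivariate treatment of repeated measures, though it does not prove it.

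**The case for a change.** The strongest reply is that the gap is real and does not depend on guessing k. The sentences are complete, so neither redaction nor file conversion explains the missing names. With uncorrelated changes the pooled time test keeps 1/(1 + k²) for LESS and k²/(1 + k²) for BESS. These shares sum to one, so at every k at least one score keeps no more than half. At k = 0.5, LESS keeps 80% but BESS only 20%. If BESS alone shifts by 0.3 SD at N = 80, the pooled time test is significant in 45%, 65% and 70% of trials at k = 1, 2 and 3. A few sentences would remove the doubt.

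That arithmetic stands, and so does the point that the analysis cannot be reproduced from the text alone. What does not follow is that the pooled test was run. The loss needs two things together: measure as the factor, and a correction that is not a joint test. The text leans against the first, and the word multivariate leaves room for a joint test if the first were true. Even then the interaction recovers part of the loss. A significant interaction could also be followed by comparisons within each score, so the post hoc intervals need not describe a mixture.

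**Conclusion.** The concern does not call for a change. The Statistical Analysis Plan leaves out the two-level factor, the form of the correction and the omnibus alpha, but this is missing detail. The reading best supported by the text, gender by time fitted separately to LESS and BESS, is sound for a descriptive objective in a case series, and so is a joint test of both scores. Under either, writing the names down would alter no result.

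The only harmful reading is measure by time without a joint test, and nothing in the documents shows that it was used. Its cost, 50% to 10% of the LESS information kept in the time test, rests on an assumed k of 1 to 3 and uncorrelated changes. Other assumptions widen this to about 4% to 80%. Refitting would be needed only if that analysis had been done.

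One caution for reading the results: if alpha was 0.05 with no adjustment, the error rate is about 5% per test. That is about 10% within a score when time and interaction are both tested, and about 16% to 19% across the two scores.

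### Pairwise PRE/MID/POST intervals are planned only after a significant ANOVA, so a non-significant LESS or BESS result has no planned estimate of change

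*Combined protocol and SAP*

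**What the plan says.** The Objective section states the aim as to "longitudinally evaluate multiple aspects of neuromuscular control (i.e., movement quality, balance) across several time points during a single athletic season". The Design section calls the study a prospective, experimental case series and adds: "We collected neuromuscular control data at three time points (PRE, MID, POST) during each athletic season". No athletes without the training are described as a comparison group.

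The Statistical Analysis Plan analyses LESS and BESS by a 2×3 ANOVA. The three-level factor is time; the two-level factor is not named. It adds that "we used a multivariate correction for these analyses", without defining the correction, and ends: "Post hoc pairwise comparisons were evaluated for significant results using 95% confidence intervals". That is the only mention of a confidence interval. No section plans a mean change, effect size or interval for an outcome whose ANOVA is not significant. No sample size, SD, correlation, test alpha or equivalence margin is given.

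**The concern.** The study's main quantity is how far each score moves between PRE, MID and POST within athletes. The plan provides an interval for that movement only when a test has already found change. A non-significant outcome can arise because scores were stable or because a modest change was missed. The plan supplies a p-value in both cases and no interval to help tell them apart.

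Stability would be informative here, because the plan itself cites variability over time in athletes who do not train this way. A stable outcome is also the one most likely to be left without a planned interval.

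A secondary effect is that intervals which appear only after significance are selected. When the true change is small, they lie too far from zero on average.

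**Working it through.** The plan states no figure to reproduce, so the check shows how the rule behaves over assumed inputs.

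**Inputs from the documents.** Three time points, hence three paired differences per outcome; two outcomes (LESS, BESS); 95% intervals; pairwise comparisons only after a significant result.

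**Assumed inputs.** One group; two-sided alpha 0.05; equal SD at each time point; central case N = 50 and within-athlete correlation r = 0.6; range N 30–90 and r 0.4–0.8; true PRE–POST change d (in SD units) with MID halfway; significance judged by a multivariate (Hotelling) test of time within one outcome.

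**Step 1: how often no interval is planned.** The test follows a noncentral F with (2, N−2) df. For a linear change the noncentrality is λ = N·d² / [2(1−r)].

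- Central case, d = 0.3: λ = 50 × 0.09 / 0.8 = 5.625. The test is significant in 52.7% of studies (simulation 52.2–52.3%), so no interval is planned in about 47–48%.
- N = 30, r = 0.4: λ = 30 × 0.09 / 1.2 = 2.25. Significant in 23%; no interval in 77%.
- N = 90, r = 0.8: λ = 90 × 0.09 / 0.4 = 20.25. Significant in 98%; no interval in 2%.
- d = 0: no interval in 95%, whatever N and r.

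**Step 2: what the missing interval would show.** Half-width = t(0.975, N−1) × √[2(1−r)/N].

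- N = 50, r = 0.6: 0.254 SD.
- N = 30, r = 0.4: 0.409 SD.
- N = 90, r = 0.8: 0.132 SD.

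Among non-significant studies in the central case, the PRE–POST interval averages −0.25 to 0.25 SD when there is no true change and −0.06 to 0.46 SD when the true change is 0.3 SD. The intervals overlap but tell the reader different things; a bare non-significant result does not.

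**Step 3: selection among the intervals that do appear** (central case, simulated).

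| True change (SD) | Test significant | Mean estimate if significant (SD) | 95% interval coverage if significant |
|---|---|---|---|
| 0.1 | about 10% | about 0.26 | about 72% |
| 0.2 | 26% | 0.34 | 90% |
| 0.3 | 52–53% | 0.39 | 95% |
| 0.5 | 94% | 0.51–0.52 | 97% |

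Over the range of N and r, coverage at 0.1 SD runs from about 57–58% to 90%. Taken over all studies, significant or not, the estimate is unbiased and coverage is 95%.

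**Step 4: sensitivity to the two-level factor.** A separate simulation with two equal groups, still testing time only, gives the same pattern. For a true change of 0.3 SDs of the change score, no interval is planned in 82%, 65%, 49% and 24% of studies at N = 20, 40, 60 and 100.

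**Step 5: the cost of always reporting.** With no true change (N = 50, r = 0.6), at least one of the three unadjusted intervals excludes zero in about 12% of studies per outcome, against 5% for the ANOVA. Among studies with a non-significant ANOVA it is about 8%.

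**The case against.** Making post hoc comparisons wait for an overall test is conventional and controls error. That stands: simulated familywise error for time under this rule is 4.8–5.2% per outcome. A reader might infer that the plan lacks multiplicity control. The concern does not show that. Whether the multivariate correction reaches the pairwise comparisons is unsettled by the text, and nothing here depends on it.

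A reader might also infer that the authors withheld estimates for non-significant outcomes. The plan says what was evaluated, not everything that was reported, and it does not rule out means or intervals by time point. The supportable statement is that no such interval is planned. The sentence could even be parsed as saying that the comparisons were inspected for significance by means of intervals. Its place after the ANOVA and the words post hoc make the conditional reading the natural one, and clearer wording would settle it.

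It is fair to say that the magnitudes are not about this study. Every numerical input beyond the three time points and the 95% level is assumed, and a range of 2–77% settles little. The one-group model also omits any interaction with the unnamed factor.

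The strongest objection concerns selection. For an outcome that is significant, the estimate and interval are the same numbers whether or not other outcomes also receive intervals. A reader might infer that always reporting would correct an overstated significant result. It would not; it only makes the full set of reported intervals unselected. For that reason selection is secondary here.

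**Conclusion.** The concern holds in limited form. By its stated rule, and not merely by silence, the plan ties pairwise intervals to significance, so a non-significant LESS or BESS result has no planned estimate of change. Under the assumed inputs this would affect about 48% of studies with a true 0.3 SD PRE–POST change. The wide range reflects the missing N and correlation. Selection matters mainly for true changes of about 0.2 SD or less; by 0.3 SD in the central case there is little coverage loss, although the mean estimate (0.39 SD) is still high.

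A further stronger reading is that an interval would let the study conclude no change. The documents state no equivalence margin, so an interval would inform that question without settling it. The change should be made; confidence is medium because the size for this study cannot be established.

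**What to change.** For LESS and for BESS, report the mean paired within-athlete differences PRE–MID, PRE–POST and MID–POST with 95% intervals, whatever the ANOVA result. If the two-level factor is between athletes and the interaction is of interest, also give them by level of that factor. Keep the significance test as the basis for any claim of change.

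Wording such as the following would do: *Paired differences between time points are given with 95% intervals for both outcomes regardless of the ANOVA result; these intervals are unadjusted estimates, not tests.* Because the plan is written in the past tense, intervals added to a completed analysis should be labelled post hoc.

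The work is six paired differences (2 outcomes × 3) from existing data, more if given by level, and a sentence or two of text. The drawback is the 12% and 8% figures above: read as tests, the unadjusted intervals would find change too often. If that is a worry, simultaneous intervals at 98.3% (1 − 0.05/3) are an option, at about 22–24% more width.
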